6.2.2 Analysis of binary (and categorical) data

6.2.2.1 Summary statistics for binary and categorical data

Summary statistics for discrete variables will be presented in contingency tables and will include count and frequency in each category. If applicable, confidence intervals will be derived as well based on the score method including continuity correction [Newcombe (1998)]:

With z as (1-alpha/2)-quantile of the standard normal distribution (SAS: $z=\text{PROBIT}(1-\text{alpha}/2)$), n as total number of subjects (i.e. number of subjects in the denominator), and p as estimated crude incidence (number of subjects with event / n) it is $q=1-p$

Then the lower limit is

$$L = \max \left(0, \frac{2np + z^2 - 1 - z\sqrt{z^2 - 2 - \frac{1}{n} + 4p(nq+1)}}{2(n+z^2)} \right)$$

and the upper limit is

$$U = \min \left(1, \frac{2np + z^2 + 1 + z\sqrt{z^2 + 2 - \frac{1}{n} + 4p(nq-1)}}{2(n+z^2)} \right).$$

In addition, if $L > p$ then $L = p$ and if $U < p$ then $U = p$.

For binary response variables (e.g. for ACR20/50/█, HAQ-DI responder, PASI 75, █) the placebo-adjusted response rates including 95% confidence interval will be derived.

SAS code for risk difference:

```
Proc freq data=acr order=formatted;
```

```
Tables response*trt/ riskdiff;
```

```
Run;
```

(Note the response value should be sorted with '1' ahead of '0'.)

Fisher's exact test will be applied to rare events (e.g., MCR), pairwise treatment group comparisons to placebo or active controls.

SAS code for Fisher's exact test:

```
Proc freq data=mcr order=formmatted;
```

```
Tables response*trt/Fisher;
```

```
Run;
```

Figures will be provided for primary and secondary variables, with means and 95% confidence intervals displayed across time for all the treatment groups.

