5.2 Treatment arms

Subjects will be randomly assigned to one of two treatment Groups in a 1:1 ratio, with approximately 425 subjects planned for each group. Subjects in Group 1 will receive secukinumab 300 mg, subjects in Group 2 will receive adalimumab 40 mg.

- Group 1:
 - --secukinumab 300 mg s.c.: 2 x 1.0 mL PFS (150 mg)
- Group 2:
 - --adalimumab 40 mg s.c.: 0.4 mL PFS (40 mg)

In order to maintain the blind, both groups will receive the same number of s.c. injections of active and/or placebo at each dosing visit throughout the study, as follows:

If the subject is allocated to Group 1, they will receive secukinumab 300 mg as two PFS, or one placebo 1mL PFS at specified visits as shown in Table 5-1 below.

If the subject is allocated to Group 2, they will receive adalimumab 40 mg as one PFS, or one adalimumab PFS and one placebo 0.5mL PFS, or two placebo 0.5mL PFS at specified visits as shown in Table 5-1 below.

Table 5-1 Blinding scheme

								St	tud	y d	osir	ıg v	isit	ts (i	n w	eek	ks, i	froi	n r	and	lom	iza	tio	n)						
Treatment assignment/ study drug administration		(,		·	7	,	O	01		1.1	,	10	00	00	7.0	70	90	30	23	2.4	3.6	3.0	40	10	4.4	16	40	60	63
Group 1 secukinumab 300mg	secukinumab 300mg 1ml PFS	2	2	2	2	2		2		2		2		2		2		2		2		2		2		2		2		
	Placebo 1ml PFS						1		1		1		1		1		1		1		1		1		1		1		1	
Group 2 adalimumab 40mg	adalimumab 40mg 0.4ml PFS	1		1		1	1	1	1	1	1	1	1	1	1	1	1	1	1	1	1	1	1	1	1	1	1	1	1	
	Placebo 0.5ml PFS	1	2	1	2	1		1		1		1		1		1		1		1		1		1		1		1		

Site staff and patient may agree on home administration at some visits as per Table 6-1 (Assessment schedule).

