^{*} power does not consider dependence of the endpoints in the Testing Strategy, power for PASI90 and enthesitis is based on the assumption that a subset of half of the population (213 subjects per group) has data of these two endpoints.

10 Ethical considerations

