6.2.2.2 Logistic regression

Certain binary outcome variables, e.g. response outcomes, will be evaluated using a logistic regression model with treatment regimen, weight, stratum if applicable. Odds ratios will be computed for comparisons of AIN457 regimen versus control(s) utilizing the logistic regression model fitted.

SAS code for logistic regression:

```
proc genmod data = acr20 descending;
class trt_ ;
model aval = trt_ weight / link=logit dist=bin;
lsmeans trt_ / diff;
estimate 'AIN457 300 mg vs ADA 40 mg' trt_ 1 -1;
ods output Estimates=imp_est;
run;
```

Logistic regression will be applied to response variables at each visit.

In cases where logistic regression doesn't converge, Fisher's exact test will be applied for comparisons of between AIN457 doses. In this case, no odds ratios or confidence intervals will be estimated, but p-values may be calculated.

```
Proc freq data=aaa;
Table TRT * AVAL / fisher;
Where TRT in ("AIN457 300 mg", "ADA 40 mg");
Run;
```

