The transformed binomial proportion estimates and standard errors are combined by applying Rubin's rules for multiple imputed data sets.

```
proc mianalyze data=logit;  
  by treat visit ;  
  modeleffects lmean;  
  stderr lse;  
  ods output ParameterEstimates=logitres;
```

```
run;
```

The combined data should be transformed back using the following formula: $p=1/(1+\exp(-y))$

```
data miexpres;
```

```
set logitres;
```

```
by treat visit ;
```

```
resti = 1/(1+exp(-estimate));
```

```
rllow = 1/(1+exp(-lclmean));
```

```
rupp = 1/(1+exp(-uclmean));
```

```
run;
```

Of note, sometimes all responses may be imputed to 0 or 1 at a given combination of response variable, treatment group and visit. Such cases should be considered separately. The combined final response rate would be the same as the original response but the 95% CI will be undefined.

The odds ratio will be derived using GENMOD for each imputation, then combined using Rubin's rules again.

```
proc genmod data = acr20_mi descending;
```

```
by avisitn _imputation_;
```

```
class trt_;
```

```
model aval = trt_ weight / link=logit dist=bin;
```

```
lsmeans trt_ / diff;
```

```
estimate 'AIN457 300 mg vs ADA 40 mg' trt_ 1 -1;
```

```
ods output Estimates=imp_est;
```

```
run;
```

```
proc mianalyze data=imp_est;
```

```
by avisitn trt_;
```

```
modeleffects LBetaEstimate;
```

```
stderr StdErr;
```

```
ods output ParameterEstimates=_res;
```

```
run;
```

The MI code for the resolution of enthesitis XXXXXXXXXX is as follows:

```
proc mi data=enthr seed=4572366 nimpute=100 out=enthr_mi;
```

```
class Baseline Week_2 Week_4 Week_8 Week_12 Week_16  
Week_20 Week_24 Week_28 Week_32 Week_36 Week_40  
Week_44 Week_48 Week_52;
```

```
by trt01p;
```

```
fcs logistic( Baseline Week_2      Week_4      Week_8      Week_12      Week_16
              Week_20      Week_24      Week_28      Week_32      Week_36      Week_40
              Week_44      Week_48      Week 52 /details) reg( weight/details);

var weight Baseline Week_2      Week_4      Week_8      Week_12      Week_16
           Week_20      Week_24      Week_28      Week_32      Week_36      Week_40
           Week_44      Week_48      Week 52;

run;
```

Details of Implementation

Steps in implementing MI and monotherapy response for binary variables (except for resolution of enthesitis [REDACTED]).

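### The SAP's risk-difference code puts response in the rows, so it does not estimate the secukinumab-minus-adalimumab difference in response rates (minor code and wording correction)

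*SAP*

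**What the plan says.** SAP 6.2.2.1 (summary statistics for binary and categorical data) states that for binary responses, with ACR20/50, HAQ-DI responder and PASI 75 among its examples, "the placebo-adjusted response rates including 95% confidence interval will be derived". The code follows under the label "SAS code for risk difference": a PROC FREQ call with formatted ordering and the statement "Tables response*trt/ riskdiff". A note asks for response 1 to be sorted ahead of 0.

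Three other places bear on it:

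- SAP 6.2.2.2 gives a Fisher fallback with treatment in the rows: "Table TRT * AVAL / fisher". The Fisher code in 6.2.2.1 has response in the rows.
- SAP 6.2.2.4 covers pooling of each arm's response rate ("The transformed binomial proportion estimates and standard errors are combined by applying" Rubin's rules) and of the odds ratio ("The odds ratio will be derived using GENMOD for each imputation"). It does not mention the risk difference.
- Protocol 5.2 says "Subjects will be randomly assigned to one of two treatment Groups in a 1:1 ratio". The groups are secukinumab 300 mg and adalimumab 40 mg.

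**The concern.** The text leads the reader to expect an absolute between-arm difference in response rates with a 95% confidence interval. With response in the rows, the code conditions on the outcome. For the secukinumab column it estimates P(secukinumab | responder) − P(secukinumab | non-responder), with the interval for that quantity. The intended quantity is P(response | secukinumab) − P(response | adalimumab). The sort note fixes the order of the levels but does not exchange rows and columns.

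Three smaller gaps go with it:

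- The SAP does not say which of the two printed column differences is reported.
- The text adjusts for a placebo that the trial does not have.
- The SAP text does not say how the difference and its interval are combined over the 100 imputations.

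At stake is a descriptive table. A programmer who followed the code would label one quantity as another.

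**Working it through.** **Inputs.** Planned rates, secukinumab vs adalimumab, from Protocol 9.7 and SAP section 3: ACR20 62% vs 50%; ACR50 49% vs 38%; PASI90 63% vs 38%; resolution of enthesitis 61% vs 33%. Group sizes are 425 per arm, or 213 per arm for PASI90 and enthesitis under the plan's half-population assumption. How RISKDIFF works is standard software behaviour and is not stated in the documents.

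**The plan's own figure.** Chi-square power for ACR20, with p̄ = 0.56:

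Φ{[0.12·√425 − 1.96·√(2·0.56·0.44)] / √(0.62·0.38 + 0.50·0.50)} = Φ{(2.474 − 1.376)/0.697} = 94.2%

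This reproduces the stated 94%, so the inputs are read correctly. The plan gives no figure for the risk-difference output itself.

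**ACR20, expected counts.**

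- Responders: 425·0.62 + 425·0.50 = 263.5 + 212.5 = 476.
- Non-responders: 161.5 + 212.5 = 374.
- As coded: 263.5/476 − 161.5/374 = 0.5536 − 0.4318 = 12.18 points.
- Intended: 0.62 − 0.50 = 12.00 points.

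**General form for equal arms.** With d = p1 − p0 and p̄ the mean of the two rates:

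p1/(p1+p0) − (1−p1)/(2−p1−p0) = d / [4·p̄·(1−p̄)]

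| Endpoint | 4p̄(1−p̄) | As coded, points (Wald 95% CI) | Intended, points (Wald 95% CI) | Gap |
|---|---|---|---|---|
| ACR20 | 0.9856 | 12.18 (5.46–18.89) | 12.00 (5.37–18.63) | 0.175 |
| ACR50 | 0.9831 | 11.19 (4.45–17.92) | 11.00 (4.38–17.62) | 0.189 |
| Enthesitis | 0.9964 | 28.10 (18.98–37.23) | 28.00 (18.90–37.10) | 0.101 |
| PASI90 | 0.9999 | 25.00 (15.81–34.20) | 25.00 (15.81–34.19) | 0.003 |

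**How far the near-agreement reaches.** The gap is at most e when |1 − 2p̄| ≤ √[1 − d/(d+e)]. For d = 12 points:

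- e = 0.5 gives √0.04 = 0.20, so p̄ from 40.0% to 60.0%.
- e = 1 gives √(1/13) = 0.277, so p̄ from 36.1% to 63.9%.

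The planned overall ACR20 rate of 56% lies inside both ranges. Outside them the gap grows. The next three pairs of rates are assumptions, not taken from the documents, with 425 per arm: 20% vs 10% gives 19.6 points instead of 10.0; 90% vs 80% also gives 19.6 instead of 10.0; 10% vs 5% gives 18.0 instead of 5.0.

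**Sign.** In a 2×2 table the two column differences are equal in size and opposite in sign. The positive values above assume the secukinumab column. If the treatment labels are those in SAP 6.2.2.2, formatted ordering puts the adalimumab label first, and column 1 would show −12.18 for ACR20.

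**Can the interval be recovered elsewhere?** With complete data, the delta method on the two arms' logit rates and standard errors (the scale used in SAP 6.2.2.4) gives 12.00 (5.37–18.63) for ACR20. This equals the direct Wald result. A correct interval is therefore obtainable, but the SAP text does not say that it will be obtained this way.

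**The case against.** The best case against raising this is that it changes almost nothing. SAP 2.6.1 evaluates the primary estimand by the odds ratio. H1, H2, H3 and H5 are tested by logistic regression and H4 by MMRM. The code sits among summary statistics, and at planned rates the gap is under 0.2 points. That stands, and it is why the point is minor. Protocol 9.4.3, however, frames the estimands as a difference in proportions, so the output is not idle.

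The wording around the code is generic, and reading it as secukinumab minus adalimumab is an inference. That is fair, but with two arms no other between-arm difference is available.

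The contrast between the Fisher blocks proves little, since Fisher's p-value is unchanged by transposing the table and the Fisher code in 6.2.2.1 shares the criticised orientation. This also stands. The contrast shows only that the SAP has no settled orientation. The error follows from RISKDIFF alone.

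The silence on pooling is weaker ground. The SAP's numbering passes from section 4 to section 6, and section 2.9.1 cites a section 5.2.4.1 that is not in the text, so pooling may be described elsewhere. It is a point to clarify and does not carry the finding.

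Finally, the 0.2-point figure does not bound all output. The documents give no planning rates for HAQ-DI responder or PASI 75, both named in 6.2.2.1, and the psoriasis and enthesitis subsets need not be equal in size. This is correct, and it argues for making the fix.

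**Conclusion.** The concern holds. Followed as written, the risk-difference code reports a different quantity, with a different interval, from the difference in response rates. The severity is minor. At the planned Week 52 rates with equal arms the largest error is 0.19 points (ACR50), and each pair of intervals leads to the same conclusion. No test, odds ratio, alpha allocation or sample size is affected.

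The conclusion rests on standard PROC FREQ behaviour. The small size rests on 1:1 allocation and overall response near 50%. For visits or endpoints well away from 50% the displayed difference could be visibly wrong. The placebo wording is wrong in any case.

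**What to change.** In SAP 6.2.2.1:

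- Replace the statement with `tables trt*response / riskdiff`. Set the treatment order explicitly so that secukinumab is row 1 and the result is secukinumab minus adalimumab. Transposing alone does not secure the sign.
- State that the column for response = 1 is the one reported.
- Run the step by `_imputation_`, and pool the difference and its standard error with Rubin's rules. If pooling is described elsewhere, cite that place.
- Describe the result as the secukinumab-minus-adalimumab difference in response rates, and drop the reference to placebo.

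The cost is a few lines of code and text. At planned rates with equal arms the reported differences move by at most about 0.2 points, and nothing in the confirmatory analysis changes.

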6.2.2.2 Logistic regression

Certain binary outcome variables, e.g. response outcomes, will be evaluated using a logistic regression model with treatment regimen, weight, stratum if applicable. Odds ratios will be computed for comparisons of AIN457 regimen versus control(s) utilizing the logistic regression model fitted.

SAS code for logistic regression:

```
proc genmod data = acr20 descending;
class trt_ ;
model aval = trt_ weight / link=logit dist=bin;
lsmeans trt_ / diff;
estimate 'AIN457 300 mg vs ADA 40 mg' trt_ 1 -1;
ods output Estimates=imp_est;
run;
```

Logistic regression will be applied to response variables at each visit.

In cases where logistic regression doesn't converge, Fisher's exact test will be applied for comparisons of between AIN457 doses. In this case, no odds ratios or confidence intervals will be estimated, but p-values may be calculated.

```
Proc freq data=aaa;
Table TRT * AVAL / fisher;
Where TRT in ("AIN457 300 mg", "ADA 40 mg");
Run;
```

6.2.2.3 Cochran-Mantel-Haenszel Test

The CMH test will be performed using the SAS procedure PROC FREQ with the CMH option.

6.2.2.4 Multiple Imputation

A multiple imputation will be performed based on MAR by treatment group for baseline weight, baseline and post-baseline of each parameter for visits up to the primary time point (Week 24) using Markov Chain Monte Carlo (MCMC) method with EM algorithm.

Impute the missing values 100 times (NIMPUTE) with a seed=457<studycode> for each component necessary to calculate the final score as shown below:

```
proc mi data= out=imp min= &minval max= &maxval minmaxiter=1000000 nimpute=100
seed=4572366;
by trt;
var weight_base Baseline Week_2 Week_4 Week_8 Week_12
Week_16 Week_20 Week_24 Week_28 Week_32 Week_36
Week_40 Week_44 Week_48 Week_52;
```

```
mcmc chain=multiple initial=em;
```

```
run;
```

where &minval and &maxval refer to minimum and maximum imputed values. For tender joint, minval=0, maxval=78; For swollen joint, minval=0, maxval=76; For VAS scores, minval=0, maxval=100; For CRP and ESR, minval=0, maxval= (no maximum value); For PASI total score, minval=0, maxval= 72; For ██████████, minval=0, maxval=10; For ██████████, minval=0.96, maxval=9.4 (Hansen et al 2017); For mCPDAI, minval=0, maxval=12; For ██████████, minval=0, maxval=164 . By defining the min and max during imputation, each variable will be confirmed to be within the range of its scale. The imputation of CRP and ESR will be based on $\log(\text{value}+1)$ and will be converted back to original value scale after imputation.

The score and ACR response can now be calculated based on the complete data. The response rate will be calculated for each imputation and then combined using Rubin's rules.

In order to calculate the response rate for each imputation, PROC FREQ will be used as follows.

Calculate binomial proportion and standard error for each imputation.

```
proc freq data=<ACR20>;  
  by treat visit _imputation_ ;  
  tables <response> / binomial (level=2 cl=wilson correct) ;  
  ods output BinomialProp=imp_bpr;  
run;
```

Transpose the dataset for subsequent use with PROC MIANALYZE.

```
proc transpose data=imp_bpr out=imp_trs(drop=_name_) ;  
  by treat visit _imputation_ ;  
  var nvalue1; id name1; idlabel label1;  
run;
```

Apply LOGIT transformation: $y=\log(p/(1-p))$ and std. err. transformation: $\text{<new se>} = \text{se}/(p*(1-p))$

```
data logit;  
  set imp_trs(rename=( _bin_ =p e_bin=se));  
  by treat visit _imputation_ ;  
  lmean=log(p/(1-p));  
  lse=se/(p*(1-p));  
run;
```

The transformed binomial proportion estimates and standard errors are combined by applying Rubin's rules for multiple imputed data sets.

```
proc mianalyze data=logit;  
  by treat visit ;  
  modeleffects lmean;  
  stderr lse;  
  ods output ParameterEstimates=logitres;
```

```
run;
```

The combined data should be transformed back using the following formula: $p=1/(1+\exp(-y))$

```
data miexpres;
```

```
set logitres;
```

```
by treat visit ;
```

```
resti = 1/(1+exp(-estimate));
```

```
rllow = 1/(1+exp(-lclmean));
```

```
rupp = 1/(1+exp(-uclmean));
```

```
run;
```

Of note, sometimes all responses may be imputed to 0 or 1 at a given combination of response variable, treatment group and visit. Such cases should be considered separately. The combined final response rate would be the same as the original response but the 95% CI will be undefined.

The odds ratio will be derived using GENMOD for each imputation, then combined using Rubin's rules again.

```
proc genmod data = acr20_mi descending;
```

```
by avisitn _imputation_;
```

```
class trt_;
```

```
model aval = trt_ weight / link=logit dist=bin;
```

```
lsmeans trt_ / diff;
```

```
estimate 'AIN457 300 mg vs ADA 40 mg' trt_ 1 -1;
```

```
ods output Estimates=imp_est;
```

```
run;
```

```
proc mianalyze data=imp_est;
```

```
by avisitn trt_;
```

```
modeleffects LBetaEstimate;
```

```
stderr StdErr;
```

```
ods output ParameterEstimates=_res;
```

```
run;
```

The MI code for the resolution of enthesitis XXXXXXXXXX is as follows:

```
proc mi data=enthr seed=4572366 nimpute=100 out=enthr_mi;
```

```
class Baseline Week_2 Week_4 Week_8 Week_12 Week_16  
Week_20 Week_24 Week_28 Week_32 Week_36 Week_40  
Week_44 Week_48 Week_52;
```

```
by trt01p;
```

```
fcs logistic( Baseline Week_2      Week_4      Week_8      Week_12      Week_16
              Week_20      Week_24      Week_28      Week_32      Week_36      Week_40
              Week_44      Week_48      Week 52 /details) reg( weight/details);

var weight Baseline Week_2      Week_4      Week_8      Week_12      Week_16
           Week_20      Week_24      Week_28      Week_32      Week_36      Week_40
           Week_44      Week_48      Week 52;

run;
```

Details of Implementation

Steps in implementing MI and monotherapy response for binary variables (except for resolution of enthesitis [REDACTED]).

1. For each continuous component (or total score for PASI, [REDACTED]) dataset, set the data collected after patient discontinued study treatment to missing.
2. For each continuous component (or total score for PASI, [REDACTED]) dataset, set data collected after patient took cDMARDs after Week 36 to missing.
3. Apply multiple imputation to create multiple sets of complete dataset
4. Calculate the binary endpoint for each complete dataset.
5. Set as non-response for the visits after the End of Treatment visit (i.e. if End of Treatment happened at Week 16, all visits after Week 16 will be set as non-response).
6. Set as non-response for the visits after the visit when patient took cDMARDs after Week 36 (i.e. Study day 274, the upper limit of analysis visit window of Week 36).
7. Set as non-response for the visits after the visit of unblinding before end of study date.
8. Proceed with the analysis.

Steps in implementing MI and monotherapy response for resolution of enthesitis [REDACTED]:

1. Set data collected after patient discontinued study treatment to missing.
2. Set data collected after patient took cDMARDs after Week 36 to missing.
3. Apply multiple imputation to create multiple sets of complete dataset.
4. Set as non-response the visits after the End of Treatment visit (i.e. if End of Treatment happened at Week 16, all visits after Week 16 will be set as non-response)
5. Set as non-response the visits after the visit when patient took cDMARDs after Week 36 (i.e. Study day 274, the upper limit of analysis visit window of Week 36)
6. Proceed with the analysis

6.2.3 Crude incidence and related risk estimates

6.2.3.1 Crude incidence and 100*(1- α)% confidence interval

For n subjects, each at risk to experience a certain event with probability π , the crude incidence is estimated as $p=x/n$, where x is the number of subjects with the event.

Absolute and relative frequencies will be displayed as well as 95% confidence interval for the relative frequency based on the score method including continuity correction (Newcombe 1998).

With z as $(1-\alpha/2)$ -quantile of the standard normal distribution (SAS: $z=\text{PROBIT}(1-\alpha/2)$), n as total number of subjects (i.e. number of subjects in the denominator), and p as estimated crude incidence (number of subjects with event / n) it is $q = 1 - p$.

Then the lower limit is

$$L = \max \left(0, \frac{2np + z^2 - 1 - z \sqrt{z^2 - 2 - \frac{1}{n} + 4p(nq + 1)}}{2(n + z^2)} \right)$$

and the upper limit is

$$U = \min \left(1, \frac{2np + z^2 + 1 + z \sqrt{z^2 + 2 - \frac{1}{n} + 4p(nq - 1)}}{2(n + z^2)} \right).$$

In addition, if $L > p$ then $L = p$ and if $U < p$ then $U = p$.

[figure not shown]
If appropriate, an exact $100*(1-\alpha)\%$ confidence interval (Clopper-Pearson 1934) will be obtained by using the SAS procedure PROC FREQ with the EXACT BINOMIAL statement. However, the confidence interval derived via the score method including continuity correction will be the default in safety analyses.

[figure not shown]
